Trial randomizzato e controllato di superiorità in cieco (elaborazione dati) a gruppi paralleli con rapporto di allocazione di 1:1 con randomizzazione a blocchi di 10 e bilanciati per reparto e per area. Non è possibile la cecità degli outcome assesor in quanto nei pazienti del gruppo sperimentale resta spesso una traccia cutanea della presenza della schiuma (impronta cutanea).

Randomized controlled superiority trial (blinded only data processing) with parallel groups.

Allocation ratio of 1: 1 with randomization in blocks of 10 and balanced by department and

by area. The blindness of outcomes assesor is not possible as in the patients of the

experimental group there is often a cutaneous trace of the presence of the foam (skin

impression).

Materials and methods

Areas involved

Surgical Area: general or specialist surgery departments.

Medical Area: geriatrics or neurology or internal medicine departments.

Intensive Area: intensive care or intensive care units.

For each area of each participating center a sample of 40 subjects is expected, randomization

will be done by areas.

Intervention:

Application of MSP in the sacral region within 24 hours of admission and replaced when it

comes off, gets wet or gets dirty in addition to standard preventive care (see below).

MSP is a multilayer foam consisting of: a multi-layered dressing consisting of a polyurethane

foam and a super-absorbent hydrocapillary pad, two layers of polyurethane film, one external

and one internal, and a pressure-sensitive adhesive (PSA) that holds together the two

absorbent layers. The last layer, in contact with the lesion and the skin, is in delicate adhesive

silicone, non-adherent, perforated.

The foam must be raised to the margins at least once a day to check the condition of the

underlying skin. If on the seventh day after randomization the patient is still hospitalized,

after the inspection of the skin, the data collection form (CRF) is closed and the study

concluded.

The medication will be provided free of charge for all the subjects in the studio by the

manufacturer. The company will only supply the dressings. A written agreement was signed

in which the company agrees to provide free samples of the product being studied without

5 di 18

affecting in any way the methodology of drafting the protocol, conducting the study, analyzing the data and publishing the results.

Comparison:

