Standard preventive care. If on the seventh day after randomization the patient is still hospitalized, after the inspection of the skin, the CRF is closed and the study concluded.

Standard preventive care

Evaluation of the risk of developingPD with a Braden scale within 24 hours of admission. Positioning of the patient on a preventive or curative anti-decubitus mattress (static or alternating pressure) if Braden value ≤ 16 or in any case according to the hospital policy, daily inspection of the skin and mobilization of the patient at least every 4 hours (in the surgical patient at least in the post-operative period) if the clinical conditions allow it (NPUAP 2014). Management of incontinence, humidity control and prevention of skin maceration and rubbing / friction during postural changes as per hospital policy.

Method

At the entrance of the patient in the ward, the nurse dedicated to the first reception assesses whether the person has the necessary criteria to be enrolled in the study. In the positive case, he/she will explain to the patient or to his legal guardian, the rationale of the study, he/she will submit the information requesting consent to the participation granting the necessary time for reading and consultation before any consent and signature. If the patient consents, the nurse has the consent signed and attached to the medical record by setting the first part of the CRF (attachment). If the patient at risk refuses the participation, if he/she has other exclusion criteria or if it is not possible to collect the consent, the nurse transcribes it on the CRF and files it. If the patient agrees to participate in the study, the dedicated nurse proceeds to randomization (see below for methods) taking the first opaque envelope according to the external progressive number. It transcribes in the CRF the date, the patient's ID, if he already has PD not to the sacrum and their category and location. It also sign the study arm and other variables of interest. If the patient is in the experimental arm, the nurse, in addition to the standard preventive care, applies the MSP to the sacrum and writes date and time on the CRF and on the MPS. However, the foam must be applied within 24 hours of admission. If this

time interval is exceeded, the researcher will mark the problem in CRF in the "NOTES" part and the patient leaves the study and the CRF is archived.

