At the Research Center for Health Professions of the Rizzoli Orthopedic Institute in Bologna (coordinating center), using the site: www.randomization.com, a randomization list will be generated in blocks of 10. A sequence of opaque envelopes will be prepared with outside a progressive number. Inside the envelope a label will be placed that will contain the words "yes" or "no", according to the sequence indicated by the generated list.

The envelopes will always be sealed at the Research Center and the list kept under lock and key. The envelopes will be placed in a dedicated box and delivered to the nursing research manager of the hospitals involved in the study. In each ward/area a reference nurse will be identified and 40 envelopes delivered.

Statistical analysis

The analysis of the results will be carried out for Intention to Treat.

All continuous data will be expressed in terms of average and standard deviation. One Way ANOVA will be used to evaluate the differences between the averages of the experimental and comparison group. If the Levene test for homogeneity of variance were significant (p <0.05), the Mann Whitney test will be used. For all dichotomous variables the incidence, relative risk, relative risk reduction and number needed to treat will be calculated. The exact

Fisher test will be used to evaluate the differences between the incidences of different outcomes between the experimental group and the control group.

Subgroup analysis:

- by area of belonging (medical, surgical or intensive)
- by risk level according to the Braden classification: Severe (total score 9); High Risk (10-12) Moderate Risk (13-14); low Risk (15-16). (Pancorbo-Hidalgo PL 2006)
- by origin (domicile vs. other settings)

For all tests, a p <0.05 will be considered significant.

The statistical analysis will be done using the "Statistical Package for the Social Sciences" (SPSS) software version 15.0 (SPSS Inc., Chicago, USA)

Possible deviations from the protocol and / or critical issues and related behavior to be followed in all situations

- If the dedicated nurse, during the daily inspection, realizes that the sacral MSP (in the patients of the experimental arm) has been removed without being positioned anymore, he provides to reposition it, marking in the CRF that the patient for that day remained without.

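### A single stated block size of 10, with visible allocations and the same nurse role screening and randomizing, could let up to one allocation in six be deduced before the envelope is opened

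*Combined protocol and SAP*

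**What the plan says.** - **Block size.** The Randomization section says that "a randomization list will be generated in blocks of 10". The Design section repeats it: "Allocation ratio of 1: 1 with randomization in blocks of 10 and balanced by department and" by area. No other block size is mentioned, and nothing says that the size is withheld from the sites.
- **Envelope supply.** Under Randomization, "In each ward/area a reference nurse will be identified and 40 envelopes delivered". The Areas involved and Sample size sections set 40 patients per area in each hospital.
- **Who does what.** Under Method, "the nurse dedicated to the first reception assesses whether the person has the necessary criteria". This nurse also explains the study and obtains consent. The dedicated nurse then randomizes by "taking the first opaque envelope according to the external progressive number".
- **Visibility.** In the experimental arm "the nurse, in addition to the standard preventive care, applies the MSP to the sacrum". The Design section describes a "Randomized controlled superiority trial (blinded only data processing) with parallel groups".
- **Safeguards.** Under Randomization, "The envelopes will always be sealed at the Research Center and the list kept under lock and key". The envelopes are opaque.

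**The concern.** Sealed opaque envelopes prevent one kind of failure: reading the next allocation. They do nothing against working it out. With a constant block of 10 and a 1:1 ratio, the rest of a block is settled once five patients have gone to one arm. Envelopes numbered from 1 to 40 put the block boundaries at 10, 20, 30 and 40. Earlier allocations are no secret on a ward where the dressing is applied and checked daily.

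The person placed to make the deduction holds the role that decides whether the next patient is eligible. Some of that decision is judgement, such as the Braden score and the expected stay or life expectancy over 72 hours. Foreknowledge would allow a patient to be approached or passed over according to perceived risk. The planned comparison of incidences is an unadjusted Fisher test, so an imbalance created in this way would feed straight into the primary result. Outcome assessment is unblinded too. The protocol acknowledges and explains that; it is a separate matter. It cannot repair a problem at entry, and entry is the part that the coordinating centre can still control.

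**Working it through.** **Inputs.** Block size 10 and ratio 1:1, so 5 + 5 per block (Design, Randomization). 40 envelopes per ward/area, which is 4 blocks (Randomization). 840 patients (Sample size), which is 840/10 = 84 blocks or 840/40 = 21 lists. The plan gives no figure of its own for predictability, so there is none to reproduce.

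**Step 1: certain knowledge with blocks of 10.** There are C(10,5) = 252 equally likely blocks. The allocation made when k envelopes remain is forced if all k belong to one arm. This occurs in 2 × C(10−k, 5) blocks:

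- k = 1 (envelope 10): 252/252 = 100%
- k = 2 (envelope 9): 112/252 = 44%
- k = 3 (envelope 8): 42/252 = 17%
- k = 4 (envelope 7): 12/252 = 4.8%
- k = 5 (envelope 6): 2/252 = 0.8%

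The sum is 420/252 = 1.667 per block, or 16.7%. That is 4 × 1.667 = 6.7 of 40 per list and 84 × 1.667 = 140 of 840. The general form for a block of 2m is 2m/(m+1), here 10/6.

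**Step 2: best guess with blocks of 10.** Always guessing the arm that is behind in the block is right in a share [m + 2^(2m−1)/C(2m,m) − 0.5]/2m of cases. At m = 5 this is (5 + 512/252 − 0.5)/10 = 65.3%, against 50% by chance.

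**Step 3: how far Step 1 depends on one observer.** If two nurses each see a random half of the enrolments and share nothing, simulation gives about 0.5% certain. The plausible range is therefore from close to zero up to 16.7%.

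**Step 4: varying sizes that sum to 40, set of sizes leaked, order unknown.** Lists were simulated. An allocation was counted as certain only when every order of sizes still compatible with the allocations so far implied the same arm.

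| Sizes | Certain | Best guess |
|---|---|---|
| 10, 10, 10, 10 | 16.7% | 65.3% |
| 8, 12, 20 | about 6% (roughly 50 of 840) | 63.4% |
| 6, 10, 10, 14 | about 6.4% | about 65.1% |

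**Step 5: varying sizes, sizes unknown, but 20:20 inferred.** The 1:1 ratio and 40 envelopes remain in the protocol, so a reader may infer that a list ends 20:20. The tail of the last block is then deducible. For 8, 12 and 20 in random order the mean forced run is (8/5 + 12/7 + 20/11)/3 = (1.600 + 1.714 + 1.818)/3 = 1.71 of 40, or about 4%. For 6, 10, 10 and 14 it is (1.500 + 1.667 + 1.667 + 1.750)/4 = 1.65 of 40, also about 4%. Across 840 patients this is about 35.

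**The case against.** **The 16.7% is a ceiling.** It needs one observer who knows the block size, counts the envelopes and has seen every earlier allocation. No section says that ward nurses read the Randomization section. The phrase ward/area is ambiguous: with 40 patients per area per hospital and several department types in an area, one set may serve several wards or shifts. A reader might infer that the enrolling nurse will in fact know one allocation in six. The documents do not support that. They support an upper limit, and Step 3 shows how far below it the true share could lie. This part of the objection stands.

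**Manipulation is constrained.** Patients must be randomized within 24 hours of admission. At-risk patients who refuse, are excluded or cannot consent are recorded on a CRF. Consent and the first part of the CRF precede the envelope, and Braden score, age and origin are recorded, so imbalance can be examined. These points are fair, but they limit or reveal some uses of foreknowledge without preventing the deduction. The 24-hour limit cuts both ways, since a short delay can make a patient ineligible.

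**The remedy does little for guessing.** This also stands. Selection can act on good guesses as well as on certainty, and the guess rate moves by at most about two percentage points. A reader might also suppose that withholding the sizes removes certain knowledge altogether. It does not for lists that must end 20:20, as Step 5 shows. Freely random sizes do better on certainty (about 1.6% to 2.3% even with the set of sizes known: 8/10/12, 6/8/10 or 4/6/8), with guess rates of 64% to 68%. They give up the assurance that each list closes at 20:20.

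**Blocks of 10 are a design choice, not an internal error.** Agreed. The point is that the choice can be improved cheaply.

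**Conclusion.** The concern holds as a weakness in allocation concealment. The plan's safeguards do not address deduction from past allocations, and the single block size, numbered envelopes, visible dressing and combined screening and randomizing role make deduction possible. Up to 16.7% of allocations, at most about 140 of 840, could be known with certainty. That figure assumes knowledge of the block size and of all earlier allocations in the block. Access of ward nurses to the protocol is a reasonable inference but is not stated.

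A reader might go further and infer that selection bias occurred, or that the treatment comparison is invalid. Nothing in the documents shows either. The calculation measures predictability and gives no estimate of bias in the relative risk or the type I error. The change is worth making because it is cheap and removes most of the certain knowledge, not because the trial fails without it.

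**What to change.** - Generate each 40-envelope list from blocks of varying size in random order that sum to 40, for example 8, 12 and 20. This set is preferable to 6, 10, 10 and 14, which leaves the guess rate almost unchanged.
- Move the block sizes out of the Design and Randomization sections supplied to sites, into a document held only by the coordinating centre.
- Require the patient ID and the remaining baseline CRF items to be written before the envelope is opened. The Method section already places consent and the first part of the CRF first, but has the ID and other variables written afterwards.
- State whether a set of 40 envelopes belongs to one ward or is shared across an area.

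**Cost.** A new list from the coordinating centre, an edited sentence in each of the Design and Randomization sections, and a small change to the order of steps under Method. Completed lists still close at 20:20. A ward that stops before 40 may be less balanced: the largest imbalance within a block is 10 for a block of 20, against 5 for a block of 10.

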The rationale for the use in prevention of products useful for the treatment of pressure injuries is also described in the 2013 systematic review (Moore 2013). The incidence of PD is probably reduced through the ability of foam dressings to redistribute mechanical forces. The Guidelines of the European and United States National Pressure Ulcer Advisory Panels (EPUAP and NPUAP) also suggest that the use of foam dressings may protect parts of the body at risk of stretch injuries. The market offers different types of advanced dressings compared to the material they are made of (hydrocolloids, polyurethane foams), their thickness (single or multi-layer) and their dimensions.

Various in vitro comparative studies are available where the different abilities of the main brands of dressings are compared with the pressure redistribution (Call 2015; Matsuzaki 2015; Miller 2015), liquid management (Young 2007) and shear forces (Levy 20015 and Levy 20016) which are the main causative factors of PD development (NPUAP 2014). In these in vitro studies the material that seems to be most effective is polyurethane foam (Matsuzaki 2015; Miller 2015), especially multilayer (Black 2015).

Two systematic reviews published in 2013 and 2014 then evaluated the efficacy on patients of using advanced multi-layer polyurethane dressings in prevention to reduce the incidence of pressure injuries (Clark 2014; Moore 2013). The results of both systematic reviews, although in favor of the use of dressings, are considered by the authors to be inconclusive due to the weakness of the study design found and therefore the high risk of bias. Both reviews concluded by soliciting the production of methodologically more rigorous clinical studies (Clark 2014; Moore 2013). Recently, some trials have been published which confirm the preventive efficacy of polyurethane multilayer foams (Santamaria 2015; Kalowes 2016; Forni 2018; Santamaria 2018) but the populations investigated are very specific, limiting the generalizability of results.

AIM

The aim of the present study was to assess whether the application of a multilayered dressing made of hydrocellular polyurethane foam conformed to the sacral area (MSP) in addition to standard preventive care reduces the rate of pressure ulcer (PU) and their severity in population at risck admitted in acute care Hospital.

Study endpoint

Primary Endpoint

Incidence of PD to the sacrum of any category detected during the first 7 days of hospitalization.

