The 7-day cut off derives from the data in the literature with respect to the average times of onset of the lesions (4th day in the medical field, 5° in the surgical field and 3° in the intensive care unit) with standard deviations that allow to affirm that after 7 days in the acute patients the PD event is extremely rare (Palese 2017; Chiari 2017; Santamaria 2015). PD is defined as a damage to the skin and underlying tissues due to pressure, stretching or friction or a combination of these factors (NPUAP 2014). The incidence of PD is represented by the PD who develop during hospitalization and are not present when the patient is admitted. The injuries will be classified according to the classification defined by the guideline prepared by NPUAP 2014. (attachment).

Secondary Endpoints:

- Incidence of PD to the sacrum category ≥ II ° according to the NPUAP scale
- Skin irritation / damage due to adhesive dressing
- Day of onset of the PD
- Number of dressings used
- Number of patients who stop treatment due to discomfort caused by the dressing (withdrawal)

Other study variables / data collected

- Gender
- Age

- Origin of the patient: first aid, another ward or facility, Short Observation (OBI), Home
- Pregressed (healed) PD to the sacred
- Patient risk level measured with the Braden scale (Pancorbo-Hidalgo PL 2006)
- Days in the study
- Use of the diaper
- Use of the bladder catheter
- Use of anti-decubitus surface (static, preventive dynamics, curative dynamics and air release)
- Daily presence of the caregiver (presence at least during a meal, never, always)

Study Population

Inclusion Criteria:

- Patients at risk of developing PD measured with the Braden scale (Braden \leq 16) with intact sacral skin and / or with signs of healing from previous sacral lesions.
- Patients or legal guardians who consent to the study
- Adult patients
- . Male and female gender
- Expected hospital stay and / or life expectancy > 72 hours
- Patients hospitalized for no more than 24 hours

Exclusion criteria:

- Patients with known allergy to the products under study or with dermatological pathologies that prevent the use of topical products
- Patient with, upon entering the ward, advanced preventive dressing in the sacral region

Design

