- Operating room: when the patient is eventually taken to the operating room to undergo surgery, the operating room nurse checks if the patient at risk is enrolled in the study. At the end of the surgical intervention, when returning to the ward, if the patient belongs to the MSP arm, check if the foam has been removed (surgery often necessary to proceed with the preparation of the sterile field for spinal anesthesia and for the procedure surgery) and repositions it.
- If the patient is transferred to the intensive care unit at any time during his or her treatment, the dedicated nurse will also enclose the data collection form with the documentation, which will continue to be filled in according to the protocol written by the dedicated intensive care nurse.
- If the patient leaves the operating room directly for intensive care, it is the duty of the dedicated nurse in the ward to send the CRF to the intensive care unit to continue the study, if it is not already attached (see previous paragraph). The Intensive care nurse will collect data with the same methods and timing.
- If the patient is transferred to a ward not involved in the study, the CRF is completed and the enrollment is closed (as if he were discharged).

Daily data collection

Every morning the data collection nurse:

- Assess the patient's skin (shoulder, sacrum, elbows, heels, back, calves, thighs, ankles...) and completed the daily CRF part;
- If the patient belongs to the intervention arm (MSP), the nurse will also check daily whether the dressing is still tight, dry and clean. If the dressing is detached even partially the MSP is replaced (do not put reinforcement patches) and the change is reported in the CRF.
- Every day (once a day) in patients with MSP, it removes an edge to check if the skin of the sacrum is still intact, marking the result of the inspection in the CRF.

- If it replaces the MSP (dirty, detached or wet) it marks it in the CRF and writes the date and time on the MPS itself. The foam will however be removed upon discharge regardless of the day of admission and in any case no more than 7 days (as per the indication of maximum permanence of the MSP provided by the manufacturer).
- Upon return of the patient from the operating room, the referring nurse verifies, as soon as possible, that the patient of the intervention arm still has the polyurethane foam in the sacrum. Otherwise apply it by marking it in the CRF.

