- At discharge or on the appearance of pressure lesion on the sacrum ≥ 2nd category, the CRF is closed and the patient ends the study. If the patient has developed PD the treatment of the lesion will be performed according to the hospital policy.
- The medication will be removed, however, no later than the first 7 days of admission after which the patient ends the study.

Study exit criteria

- Withdrawal of informed consent before randomization
- Not randomized within 24 hours of admission

Conclusion of the study in the single recruited subject

- Withdrawal of consent after randomization
- The appearance of irritation to the skin caused by the dressing. The dressing is removed, reported in CRF and irritation treated as per hospital policy.
- At the request of the patient due to discomfort due to preventive medication.
- On discharge / death / transfer to ward not involved in the study before the 7th day after randomization
- After 7 days from randomization in the absence of PD to the sacrum
- The appearance of pressure injury to the sacrum higher than the first category

Sample size

From a randomized monocentric study of at-risk patients with a hip fracture where polyurethane foams were used in prevention, the incidence in the experimental group was 4.5% while in the control group of 15.4%. Similar deltas had also been identified in other trials in intensive care patients. Assuming similar results in the population subject of the present study and taking into account an alpha error of 0.05 and a beta error of 20%, it is necessary to enroll at least 228 patients at risk. In order to allow analyzes by subgroup (see the "statistical analysis" section) the sample size must be guaranteed for each area (medical, surgical, intensive).

Taking into account also a possible loss at the follow-up of 10% and also assuming a 10% withdrawal rate, the necessary sample will be 280 patients per area and therefore a total of 840 patients (420 per arm). Each hospital involved will enroll 40 patients per area involved in that specific hospital.

Randomization

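### Day of onset has no method of its own, and the only rule that fits it would compare just the patients who developed an ulcer, a comparison that randomisation does not protect

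*Combined protocol and SAP*

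**What the plan says.** The Secondary Endpoints list includes "Day of onset of the PD". The Statistical analysis section has two generic rules. Continuous data get a mean and SD, and "One Way ANOVA will be used to evaluate the differences between the averages of the experimental and comparison group"; Mann-Whitney replaces ANOVA if Levene's test gives p < 0.05. Dichotomous data get incidence, relative risk, number needed to treat and Fisher's exact test. Neither rule names day of onset. The combined document contains no time-to-event method, no censoring rule and no onset value for patients without an ulcer. Analysis by intention to treat is stated in general terms only.

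Follow-up can end early. The section on conclusion of the study for a single subject lists "On discharge / death / transfer to ward not involved in the study before the 7th day after randomization" as well as "The appearance of irritation to the skin caused by the dressing", discomfort from the dressing, and withdrawal of consent.

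Two details of the endpoint are open:

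- **Time origin.** The Primary Endpoint reads "Incidence of PD to the sacrum of any category detected during the first 7 days of hospitalization", whereas the conclusion criteria read "After 7 days from randomization in the absence of PD to the sacrum".
- **Category.** The safety section keeps patients with a category I lesion in the study, so one patient may have both a first day of any category and a later first day of category II or above.

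**The concern.** A day of onset exists only for a patient who has an ulcer. If the continuous-data rule is applied to it, the two groups compared are those in whom prevention failed. Membership is decided after randomisation by the very outcome the dressing should change, so the groups need not be alike in anything else.

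Suppose the dressing prevents early ulcers better than late ones. The remaining ulcers in the dressing arm are then later on average, although no individual onset was delayed. The reverse pattern would make the dressing appear to hasten ulcers. A significant p-value could be reported as an effect on timing that does not exist.

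The rule also takes no account of early exit, and exits for irritation or discomfort arise essentially only where a dressing is worn.

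**Working it through.** **Inputs from the plan.** The Sample size section gives 4.5% against 15.4%, alpha 0.05, power 80%, 228 patients per area before losses, 10% loss plus 10% withdrawal, and 420 per arm in total. The Primary Endpoint section gives mean onset as "4th day in the medical field, 5° in the surgical field and 3° in the intensive care unit".

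**Check of the planning rates.** With unpooled variances and a two-sided test, n per arm = (1.960 + 0.842)² × (0.154 × 0.846 + 0.045 × 0.955) / 0.109² = 114.5. This rounds up to 115 per arm, or 230 in total, against the plan's 228. Inflation gives 228 / 0.9 / 0.9 = 281.5, against 280. The rates can be used.

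**Who enters the onset comparison.**

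- Dressing: 420 × 0.045 = 18.9. Control: 420 × 0.154 = 64.7.
- No onset day: 840 − 83.6 = 756, or 90% of those randomised. The 1:1 allocation becomes about 1:3.4.
- With 20% subtracted for losses (336 per arm): 15.1 against 51.7. Successive 10% losses give 340 per arm and nearly the same counts.
- Smallest difference detectable with 80% power: 2.802 × √(1/18.9 + 1/64.7) = 0.73 SD. At an assumed SD of 1.8 days that is 1.3 days.

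**Artefact when no onset day is shifted.** Assumptions: control onset on whole days 1 to 7, bell-shaped around day 4 (the average of 4, 5 and 3), SD 1.8 (the plan gives none), overall relative risk about 0.29. Under this distribution 59.1% of control ulcers fall by day 4, with mean day 2.74, and 40.9% fall later, with mean day 5.83. If the dressing prevents a share e of the early ulcers and l of the late ones, the mean among dressing cases is

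[(1 − e) × 0.591 × 2.74 + (1 − l) × 0.409 × 5.83] / [(1 − e) × 0.591 + (1 − l) × 0.409].

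For e = 78% and l = 60% this is (0.356 + 0.954) / (0.130 + 0.164) = 4.46 days, against 4.0 in controls. The Levene, then ANOVA or Mann-Whitney, rule was simulated in 4,000 trials per scenario (Monte Carlo error at most 0.8 points):

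| Prevented early / late | Mean day, dressing vs control | Significant, 420 per arm | Significant, 336 per arm |
|---|---|---|---|
| 71% / 71% | 4.0 vs 4.0 | 4.7% | 5.0% |
| 75% / 65% | 4.3 vs 4.0 | 8.3% | 8.1% |
| 78% / 60% | 4.5 vs 4.0 | 16.0% | 13.9% |
| 85% / 50% | 4.9 vs 4.0 | 47.8% | 38.4% |

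With SD 1.5 the four results at 420 per arm are 4.5%, 9.1%, 16.1% and 44.9%.

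**Other patterns.**

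- *Either direction.* Take control ulcers as half early type (days 1 to 5) and half late type (days 3 to 7). Mainly preventing late ulcers moves the mean by −0.55 day; mainly preventing early ones moves it by +0.57 day. About 23% of trials are significant in each case.
- *Area mix.* Using the plan's means of 3, 4 and 5 days (intensive, medical, surgical), equal areas and equal control incidence, relative risks of 0.10, 0.29 and 0.48 give (0.10 × 3 + 0.29 × 4 + 0.48 × 5) / 0.87 = 4.4 days against 4.0, and about 17% of trials significant. Relative risks of 0.20, 0.29 and 0.38 give 4.2 days and about 8%.
- *Early exit alone.* Random exit of 10% to 20% in the dressing arm only, with equal prevention, gives means of 3.95 to 3.90 days and 5% to 6% significant.

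**The case against.** That only ulcer patients would be compared is an inference, since the plan names no analysis set for this endpoint. This is true. It is still the only result of applying the written rule, because nobody else has a value to enter.

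The stakes are modest. The stated aim concerns the rate and severity of ulcers, not their timing, and this is one of five secondary endpoints with no power claim. That stands and limits the weight of the point.

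Every excess above 5% comes from an assumed pattern of prevention that the documents do not establish, and the most extreme pattern should not be taken as expected. That stands too. The plan does, however, cite different onset days by area and intends to look for effects by area, so a changed mix of cases is plausible.

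Random early exit does little harm. Exit related to ulcer risk was not quantified.

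The two time origins differ by at most about a day, because randomisation must occur within 24 hours of admission, and nothing suggests the gap differs by arm. Onset reads most naturally as any category. Both are points of definition and do not drive the bias.

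Finally, a log-rank or Cox test in all patients largely re-tests incidence, and reporting onset among cases without a p-value would by itself remove the misleading test. Both remarks are fair. The time-to-event analysis is proposed as supportive because it keeps a randomised comparison for a listed endpoint.

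**Conclusion.** The concern holds and should be settled before the data are analysed. Read as written, the plan compares about 19 with 65 patients selected by the treatment's own effect and leaves out about 90% of those randomised. These counts rest only on the plan's rates and arm size.

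The size of the resulting error is not known. It is nil if early and late ulcers are prevented equally. It is 8% to 48% of trials under the unequal patterns shown, given an assumed onset distribution and no true shift in timing. The comparison also has little power to detect a real shift.

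The reach is one secondary endpoint. The Fisher comparisons of any-category and category II and above incidence, and the sample size, are not affected.

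**What to change.** State in the Statistical analysis section:

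1. Onset is analysed as time to first sacral ulcer in all randomised patients, with cumulative incidence curves and a log-rank or Cox comparison stratified by area. It is labelled supportive because it overlaps with the primary result.
2. A method for ties is named, such as Efron's or a discrete-time model on patient-days, because the skin is inspected once a day (for the dressing arm: "Every day (once a day) in patients with MSP, it removes an edge to check if the skin of the sacrum is still intact").
3. Discharge, death, transfer, and exits for irritation, discomfort or consent withdrawal are each treated as censoring or as competing events. The choice is stated, and the alternative is run as a sensitivity analysis.
4. One time origin is used, reconciling hospitalisation with randomisation.
5. Onset refers either to any category or to category II and above.
6. Mean onset day among cases is reported descriptively, without a p-value.

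The cost is wording and a little analysis time. The CRF already records the date at randomisation and the daily skin inspection, so no new data are needed. The section on Ethics Committee approval requires an amendment for changes to the statistical analysis, and the sponsor should confirm that the named SPSS version offers the chosen method. If only the minimum is wanted, item 6 removes the misleading test but leaves the endpoint without a randomised comparison.
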